3 STUDY OBJECTIVE(S) AND DESIGN

3.1 Study Objective(s)

Stage 1:

Primary Objective: To evaluate the safety and tolerability of 3 different dose levels of ASP3772 in comparison to the active comparator Prevnar 13® (PCV13) in adults 18 to 64 years of age.

Secondary Objective: To evaluate the immunogenicity of 3 different dose levels of ASP3772 in comparison to the active comparator PCV13 in adults 18 to 64 years of age.

Stage 2:

Primary Objective: To evaluate the safety and tolerability of 3 different dose levels of ASP3772 in comparison to the active comparator PCV13 in elderly 65 to 85 years of age.

Secondary Objectives:

To evaluate the immunogenicity of 3 different dose levels of ASP3772 in comparison to the active comparator PCV13 in elderly 65 to 85 years of age.

To evaluate the immunogenicity of 3 different dose levels of ASP3772 relative to the response seen following administration of PPSV23 for the serotypes not included in PCV13.

3.2 Study Design

This is a combined phase 1, first-in-human (FIH), dose-escalation (Stage 1) and phase 2, dose-finding (Stage 2) study to evaluate the safety, tolerability and immunogenicity of ASP3772 in adult subjects and in elderly subjects.

The objectives of this study are to evaluate safety, tolerability including reactogenicity and immunogenicity in adult subjects 18 to 64 years of age in Stage 1 and in elderly subjects

65 to 85 years of age in Stage 2, who are naïve to licensed or investigational pneumococcal vaccine.

The study population will consist of 3 different groups: **Group 1** - Stage 1 subjects randomized within 3 sequential cohorts to ASP3772 or PCV13; **Group 2** - Stage 2 PCV13 naïve subjects randomized within 3 sequential cohorts to ASP3772 or PCV13; and **Group 3** - Stage 2 subjects previously vaccinated with PCV13 will receive PPSV23.

To minimize the risk to subjects, a sentinel group of subjects (n = 2; 1 ASP3772:1 PCV13) will be vaccinated in each cohort prior to initiating enrollment of the full cohort. Safety data through day 7 from sentinel subjects will be evaluated by the Dose Escalation Committee (DEC) prior to enrolling the remainder of the cohort. Safety data through day 7 from all subjects within a dose cohort will be evaluated by the DEC prior to escalating to the next dose cohort within the adult and within elderly subjects. Based on the safety data through 30 days after immunization from the first 3 cohorts, the DEC will determine if Stage 2 can

commence, and if sentinel dosing is required for Stage 2. A DEC charter will detail the roles, responsibilities and procedures for decision-making.

Stage 1, Group 1: Stage 1 of the phase 1/2 design is a randomized, active-controlled, observer-blinded, dose- escalation study of the safety, tolerability and immunogenicity of the ASP3772 pneumococcal vaccine in adult subjects (18 to 64 years of age) compared with PCV13 with a 3:1 randomization (ASP3772:PCV13). The syringe used to administer PCV13 is distinct. The vaccine administrator will differ from the person evaluating reactogenicity to remove reporting bias for any reactogenicity events. Additionally, treatment assignment will be unknown to the full study team.

Subjects will be enrolled sequentially into 1 of 3 cohorts designated by escalating ASP3772 dose levels. A single dose of ASP3772 will be administered as a 0.5 mL intramuscular (IM) injection on day 1 at 1 of 3 dose levels: 1, 2 or 5 µg of ASP3772. The subjects randomized to PCV13 will receive a single injection of the standard dose of PCV13 on day 1.

Approximately 120 subjects will be enrolled in Stage 1 of the study, 40 subjects per cohort (ASP3772 n = 30 and PCV13 n = 10).

After all subjects complete dosing in Cohort 1 (low dose, 1 µg of ASP3772 or PCV13), safety (including reactogenicity) and tolerability through 7 days postimmunization will be assessed by the DEC in a blinded manner. Assessments of safety and tolerability by the DEC will occur prior to initiating the next dose group, Cohort 2 (2 µg of ASP3772 or PCV13) and then Cohort 3 (5 µg of ASP3772 or PCV13), based on safety and tolerability data through 7 days postimmunization. The DEC Charter will provide details for revealing the treatment assignment for individual subjects to DEC members, if necessary.

Safety and tolerability assessments will continue through 30 days postimmunization. Safety assessments for serious adverse events (SAEs) and medically attended adverse events (MAAEs) including potential immune-mediated medical conditions (PIMMCs) and new-onset chronic disease (NOCD) will continue through day 180 postimmunization. Data will be collected in an observer-blinded manner (vaccine recipients and those responsible for evaluation of any study endpoint will be unaware of which vaccine the subject received).

Serum samples to measure pneumococcal serotype-specific anticapsular polysaccharide (PS) immunoglobulin G (IgG) and functional opsonophagocytic activity (OPA) will be collected prior to the first study vaccination on day 1 and on day 30 postimmunization.

The design schematic for Stage 1 is shown in the table below. There will be a total of approximately 120 evaluable adults 18 to 64 years of age.

Number of Subjects per Cohort by Immunization

Cohort	Stage 1 (Group 1)			
	ASP3772	Number of Subjects	Comparator	Number of Subjects
1	1 µg	30	PCV13	10
2	2 µg	30		10
3	5 µg	30		10

PCV13: Prevnar 13

Stage 2, Group 2:

Stage 2 of the study is a dose-finding (sequentially higher doses), active-controlled, observer-blinded study with a 3:1 randomization (ASP3772:PCV13) in elderly subjects 65 to 85 years of age (Group 2). For Stage 2, Group 2 subjects the vaccine administrator will differ from the person evaluating reactogenicity to remove reporting bias for these events. Treatment assignment will also be unknown to the blinded study team.

After screening, PCV13 naïve subjects will be randomized within each cohort to receive ASP3772 or PCV13. Subjects randomized to ASP3772 will receive a single dose of ASP3772 administered as a 0.5 mL intramuscular (IM) injection on day 1, at 1 of 3 dose levels: 1, 2 or 5 µg of ASP3772 for Cohorts 4, 5 and 6, respectively. The subjects randomized to PCV13 will receive a single injection of the standard dose of PCV13.

Stage 2 will commence after the DEC has evaluated safety (including reactogenicity) data through 30 days from all cohorts in Stage 1. Dose escalation to Cohort 5 (intermediate dose, 2 µg) in Stage 2 will commence once the DEC has evaluated Stage 2 Cohort 4 (1 µg) safety (including reactogenicity) and tolerability through 7 days postimmunization. Dose escalation into Cohort 6 (high dose, 5 µg) in Stage 2 will commence once the DEC has evaluated Stage 2 Cohort 5. The DEC will review the data for each cohort in Stage 2, Group 2 in a blinded manner. The DEC Charter will provide details for revealing the treatment assignment for individual subjects to DEC members, if necessary. Randomization for Stage 2 subjects will be stratified by age (65 to 74 years of age and 75 to 85 years of age) to ensure there is a balanced number of subjects within each age cohort immunized with either ASP3772 or PCV13.

Safety and tolerability assessments including adverse events (AEs) will continue through 30 days postimmunization. Safety assessments for SAEs and MAAEs including PIMMCs and NOCDs will continue through day 180 postimmunization. Data will be collected in an observer-blinded manner (vaccine recipients and the site staff who are responsible for evaluation of any study endpoint will be unaware of which vaccine the subject received).

Serum samples to measure IgG and OPA will be collected prior to study vaccination on day 1 and postimmunization on day 30. The primary immunogenicity evaluation for dose finding is 30 days following the initial immunization.

The design schematic for Stage 2, Group 2 is shown in the table below. There will be a total of approximately 396 evaluable adult subjects from 65 to 85 years of age.

Number of Subjects per Cohort by Treatment

Cohort	Stage 2 (Group 2)			
	ASP3772	Number of Subjects	Comparator	Number of Subjects
4	1 µg	99	PCV13	33
5	2 µg	99		33
6	5 µg	99		33

PCV13: Prevnar 13

Stage 2, Group 3:

Elderly subjects previously immunized with PCV13 will be enrolled and receive the recommended booster immunization with PPSV23 only (n = 99). Prior immunization (PCV13) should have taken place no less than 10 months and no more than 2 years prior to study drug vaccination. Immunogenicity to the 11 non-PCV13 serotypes contained in PPSV23 will be evaluated. Subjects who are given PPSV23 without previous exposure to PCV13 will not be included in the immunogenicity summaries.

Safety assessments will continue through 30 days postimmunization.

Serum samples to measure IgG and OPA levels will be collected prior to study immunization on day 1 and postimmunization on day 30.

The design schematic for Stage 2, Group 3 is shown in the table below. There will be a total of approximately 99 evaluable adult subjects from 65 to 85 years of age.

Study Treatment Group	Stage 2 (Group 3) Number of Subjects
PPSV23	99

PPSV23: Pneumovax 23

3.3 Randomization

A central randomization will be used for this study. Stage 1 subjects will be randomized to receive either ASP3772 (1, 2 or 5 µg) or PCV13 with a 3:1 ratio.

Stage 2, Group 2 subjects will be randomized to receive either ASP3772 (1, 2 or 5 µg) or PCV13 with a 3:1 ratio. The randomization for Group 2 will be stratified by age (65 to 74 years of age and 75 to 85 years of age).

The randomization assignment for Stage 1 and Stage 2, Group 2 will be unavailable to anyone involved with the study with the exception of the pharmacist and vaccine administrator until all Day 30 visits have been completed. After all subjects in Stage 1 have completed Day 30, there will be a data cutoff and an interim analysis. Similarly, once all Day 30 visits for subjects in Stage 2, Group 2 have completed, there will be a data cutoff and interim analysis. Additional safety information will be collected at the Day 180 visit.

Stage 2, Group 3 subjects will have been previously given PCV13 before entering the study and will be enrolled to receive a booster vaccination with PPSV23 only on Day 1.

4 SAMPLE SIZE

In Stage 1, approximately 120 evaluable adults 18 to 64 years of age are planned to be enrolled. This sample size is considered sufficient to obtain preliminary estimates in a phase 1 study of safety and reactogenicity in the adult population, ages 18 to 64. In Stage 2, approximately 396 evaluable adult subjects from 65 to 85 years of age are planned to be enrolled to receive either ASP3772 or PCV13. For each PCV13 serotype the OPA titer¹ responses, Geometric Mean Titer (GMT) and Geometric Standard Deviation (GSD) in subjects 60 to 64 years of age administered PCV13 (Source Prevnar13® label) were assumed

to be representative of the response following immunization with ASP3772. The width of 95% confidence intervals for each serotype with 30, 100 and 150 subjects were calculated. A sample size of approximately 100 subjects at each dose level treated with ASP3772 under these assumptions was considered sufficient to provide good estimates of OPA titer⁻¹ responses. The sample size and dose level for the phase 3 study will be determined based on the responses in stage 2 elderly subjects. In Stage 2, Group 3 approximately 99 subjects are planned to be enrolled to receive PPSV23 to provide estimates of the response to non-PCV13 serotypes in an elderly population.

5 ANALYSIS SETS

In accordance with International Conference on Harmonization (ICH) recommendations in guidelines E3 and E9, the following analysis sets will be used for the analyses.

5.1 Full Analysis Set (FAS)

The Full Analysis Set (FAS) will consist of all subjects who receive an immunization in this study with either ASP3772, PCV13 or PPSV23 and have at least 1 post immunization measurement.

The FAS will be used for summaries and primary analyses of immunogenicity data.

5.2 Per Protocol Analysis Set (PPS)

The PPS will be used to assess immunologic response and will serve as a supportive analysis. The PPS will exclude the following subjects:

- Subjects who are given antibiotics within 7 days prior to the 30-day blood draw to assess immunogenicity in the ASP3772 immunization group since these may interfere with the immunogenicity assay
- Subjects who have their 30-day blood draw 14 or more days after the 30 day post immunization scheduled blood collection
- Subjects who receive immunosuppressants as this may interfere with their ability to mount a response to the vaccine
- Subjects who have newly diagnosed immunologic abnormalities within the first two weeks after receiving the immunization.

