7.2 Study Population

7.2.1 Disposition of Subjects

The following subject data will be presented:

- Disposition: number of subjects with informed consent, discontinued before randomization, randomized and immunized;
- Analysis sets: number and percentage of subjects in the safety analysis set (randomized and received an immunization, full analysis set (randomized, immunized, and at least 1 post baseline endpoint evaluation) and per protocol analysis set (if needed) (subjects who did not receive antibiotics within 7 days of their Day 30 blood draw; subjects who have their Day 30 blood draw between Day 30 and Day 44; subjects who have not received immunosuppressants; subjects who do not have newly diagnosed immunologic abnormalities within the first 2 weeks after receiving the immunization);
- Treatment discontinuation: number and percentage of randomized subjects who completed and who discontinued treatment, by primary reason for treatment discontinuation (adverse event, death, lost to follow-up, protocol deviation, withdrawal by subject, other);

- Discontinuation up to 30 days: number and percentage of randomized subjects who completed and who discontinued the 30-day investigational period, by primary reason for discontinuation (adverse event, death, lost to follow-up, protocol deviation, withdrawal by subject, other);
- Discontinuation after Day 30 up to Day 180: Number and percentage of randomized subjects who completed and who discontinued during the follow-up period (post Day 30 through Day 180), by primary reason for discontinuing during the follow-up period (adverse event, death, lost to follow-up, protocol deviation, withdrawal by subject, other); subjects in Group 3 will not be followed beyond Day 30.
- Per protocol exclusions: Number and percentage of subjects excluded from PPS by reason for exclusion defined in Section 5.2, by treatment group.

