7.7.2 Blood Sampling for Immunogenicity, Anti-biotin and T-cell Immune Response Analysis Windows

Analysis Visits	Scheduled Day in Protocol	Analysis Windows (day)
Baseline	Day 1	Last non-missing value on day 1 prior to immunization dosing
Visit 3	Day 7	Closest non-missing post immunization value to study day 7
Visit 4	Day 30	Closest non-missing post immunization value to study day 30
Visit 5	Day 180	Closest non-missing post immunization value to study day 180

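### The per-protocol antibiotic exclusion is written for the ASP3772 group only, and SAP 7.2.1 restates the same set differently (minor; wrong as written)

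*SAP*

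**What the plan says.** SAP 5.2 and protocol 7.2.2 define the PPS by the same four exclusions. The first removes "Subjects who are given antibiotics within 7 days prior to the 30-day blood draw to assess immunogenicity in the ASP3772 immunization group", on the ground that antibiotics may interfere with the immunogenicity assay. The other three (late draw, immunosuppressants, newly diagnosed immunologic abnormality) name no arm. The timing exclusion has a late limit only: "Subjects who have their 30-day blood draw 14 or more days after the 30 day post immunization scheduled blood collection".

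SAP 7.2.1 describes the PPS again, in a parenthesis within the list of disposition tables. There the set consists of "subjects who did not receive antibiotics within 7 days of their Day 30 blood draw", with no arm named, and "subjects who have their Day 30 blood draw between Day 30 and Day 44". The last item of the same section counts PPS exclusions "by reason for exclusion defined in Section 5.2".

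Four other places bear on the point:

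- The visit schedules allow the Day 30 visit from Day 28 to Day 32.
- SAP 7.7.2 takes for that visit the "Closest non-missing post immunization value to study day 30".
- Protocol 5.1.3 asks any subject treated with systemic antibiotics to have the Day 30 visit no sooner than 7 days after the last dose, in every arm.
- SAP 5.1 states that "The FAS will be used for summaries and primary analyses of immunogenicity data". The PPS is supportive, and SAP 7.1 and 7.2.1 say it is produced only if needed.

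**The concern.** A per-protocol exclusion is applied after randomisation, so it should at least fall on both sides of a comparison by the same rule. Here a subject on ASP3772 with recent antibiotics leaves the set, and a subject on PCV13 with the same exposure stays. If antibiotic in the serum distorts the reading, the distortion is cleaned from the numerator of the ASP3772/PCV13 ratio and left in the denominator. The documents give no reason for the difference: the assay concern and the delay rule in protocol 5.1.3 apply to everyone.

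The description in SAP 7.2.1 adds a second problem. Someone building the set from that text would obtain different subjects from someone working from 5.2: antibiotic-exposed comparator subjects would go, and so would draws taken on time on Days 28 and 29.

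At stake is the reliability of a supportive analysis of a secondary objective, in a trial whose Stage 2 responses inform the phase 3 dose and sample size. The primary immunogenicity results are not at stake.

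**Working it through.** **1. The antibiotic rule, text against text.** In SAP 5.2 and protocol 7.2.2 the closing phrase about the ASP3772 group can attach to the subjects or to the assessment of immunogenicity. On either attachment, only ASP3772 is named. SAP 7.2.1 names no arm. It also refers to antibiotics around the draw, where 5.2 refers to antibiotics before it.

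**2. The draw window, day by day.** SAP 7.7.2 and 7.7.3 both put the scheduled draw at study Day 30, with dosing on Day 1. Under 5.2 the first day excluded is 30 + 14 = 44, so the last day kept is 43. SAP 7.2.1 is read with inclusive bounds. Days 16 to 46 are the Day 30 window in SAP 7.7.3.

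| Draw on study day | SAP 5.2 | SAP 7.2.1 |
|---|---|---|
| 16–27 | kept | dropped |
| 28–29 (on time) | kept | dropped |
| 30–32 (on time) | kept | kept |
| 33–43 | kept | kept |
| 44 | dropped | kept |
| 45–46 | dropped | dropped |

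Of the five on-time days, 5.2 drops none and 7.2.1 drops two. With exclusive bounds, 7.2.1 would lose Day 30 as well.

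**3. How far the asymmetry could move the ratio.** The documents give neither the frequency of antibiotic use near the draw nor the size of any interference, so both are assumed. Suppose *m* of *n* pooled PCV13 subjects stay in with readings raised *k*-fold, while their ASP3772 counterparts are removed. The PCV13 geometric mean is multiplied by k^(m/n) and the ASP3772/PCV13 ratio by k^(−m/n). If readings are lowered *k*-fold, the factor is k^(+m/n). From the design tables, pooled PCV13 is 3 × 33 = 99 in Stage 2 and 3 × 10 = 30 in Stage 1.

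| Stage | m of n | k | Factor if raised | Factor if lowered |
|---|---|---|---|---|
| 2 | 1 of 99 | 2 | 0.993 | 1.007 |
| 2 | 3 of 99 | 4 | 0.959 | 1.043 |
| 2 | 5 of 99 | 10 | 0.890 | 1.123 |
| 1 | 1 of 30 | 2 | 0.977 | 1.023 |
| 1 | 2 of 30 | 10 | 0.858 | 1.166 |

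**4. Against sampling error.** The 95% confidence limits of a ratio of two geometric means lie a factor exp(t × ln(GSD) × √(2/n)) either side of the estimate. The documents do not print a geometric standard deviation (GSD), so 3 to 6 is assumed.

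- 99 against 99: 1.36 (GSD 3) to 1.65 (GSD 6).
- 30 against 30: 1.76 to 2.52.

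The largest shift in Stage 2 is 1.123 in either direction (1/0.890), below 1.36. In Stage 1 it is 1.166, below 1.76.

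**The case against.** The strongest reply is that nothing important depends on this. The primary endpoints are safety, the full analysis set carries the primary immunogenicity analyses, and the PPS is supportive and conditional. Because the 7-day delay applies to every arm, few subjects should have antibiotics inside the window at all. The arm phrase looks like loose drafting, since the other three exclusions and SAP 7.2.1 name no arm. SAP section 1 also plans a data review before hard lock to verify analysis set classification. All of this stands as a limit on size, and it is why the point is minor. It does not make the sentence right: the phrase appears in both documents and names only ASP3772 however it is parsed. Nor does the review replace a written rule. SAP 7.6 unblinds the sponsor at the Day 30 data cut, and section 1 requires only that the review come before hard lock, so it could take place with assignments known.

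Four stronger readings are tempting, and the documents do not support them.

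- *On-time subjects will be lost.* A reader might infer from SAP 7.2.1 that Day 28 and 29 draws leave the PPS. Because that section tabulates exclusions "by reason for exclusion defined in Section 5.2", 5.2 appears to govern, and 5.2 keeps those draws.
- *The late limit is undefined.* Counting 30 days on from Day 1 would give Day 31 and a last kept day of 44. SAP 7.7.2 and 7.7.3 largely settle this by scheduling the draw on study Day 30. What is left is a one-day mismatch with 7.2.1.
- *The PPSV23 comparison is biased too.* Group 3 is not randomised and its planned immunogenicity analyses are within-group estimates, so the between-arm argument does not extend to it.
- *SAP 7.7.3 cancels the timing exclusion.* Its statement that off-schedule data are not excluded is a general rule on allocating visits, and a specific PPS exclusion is normally read as prevailing.

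**Conclusion.** The point holds as a minor one. Taken literally, the antibiotic exclusion is one-sided between ASP3772 and PCV13, and its own rationale does not justify that. SAP 7.2.1 restates the set in conflict with 5.2 and with the visit window, but as a text error rather than a second operative rule.

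The direction of any bias is unknown. Under the assumed ranges (1 to 5 of 99 or 1 to 2 of 30 comparator subjects exposed, 2- to 10-fold interference, GSD 3 to 6), every shift is smaller than sampling error. A reader might go further and infer that the trial's main immunogenicity conclusions are biased, or that the sponsor meant to favour one arm. The documents support neither: the full analysis set does not use this rule, and the text does not settle whether the arm limit was intended.

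**What to change.** 1. In SAP 5.2, delete the words that confine the antibiotic exclusion to the ASP3772 group, so that it covers all arms.
2. Align protocol 7.2.2 at the next amendment, or record the SAP clarification in the clinical study report. A protocol amendment made only for this is not needed: protocol section 7 leaves analysis detail to the SAP, whereas protocol 12.1.3 requires signatures and, unless the change is administrative, ethics approval.
3. In SAP 7.2.1, replace the parenthesis describing the PPS with a cross-reference to Section 5.2. This removes the Day 30 lower bound, the Day 44 mismatch and the looser antibiotic wording together.
4. In SAP 5.2, state the existing late limit as a study day counted from the scheduled study Day 30, with Day 43 the last day kept. Add no early-draw exclusion, so that Days 28 to 32 all stay in.

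The cost is a few wording edits and no new data. A few antibiotic-exposed comparator subjects leave a supportive set, and nobody leaves for an early draw.

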- 12. Subject has/had febrile illness (> 100.4°F oral equivalent) or symptomatic, viral, bacterial (including upper respiratory infection) or fungal (noncutaneous) infection within 1 week prior to day 1.
- 13. Subject has any clinically significant abnormality following the investigator's review of the physical examination, ECG and protocol defined clinical laboratory tests during screening.
- 14. Subject is unlikely to adhere to study procedures, keep appointments, is planning to relocate during the study or cannot be adequately followed for safety according to the protocol.
- 15. Subject has any other condition, which, in the opinion of the investigator, precludes the subject's participation in the study.
- 16. Subject has received any vaccines within 30 days prior of receipt of the study vaccine (exception: Influenza virus vaccine given according to recommended guidelines must be given at least 7 days prior to receiving study vaccine).
- 17. Subject has had significant blood loss, donated 1 unit (450 mL or more) or received transfusion of any blood or blood products within 60 days or donated plasma within 7 days prior to day 1.
- 18. Subject has received any systemically absorbed antibiotics during the 7-day period prior to day 1.

Waivers to the exclusion criteria will **NOT** be allowed.

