5.1.3 Previous and Concomitant Treatment (Medication and NonMedication Therapy)

Subjects will not be allowed to take immunizations, blood product, immunosuppressants including systemic steroids (topical steroids will be allowed) from first study vaccine administration until 30 days postimmunization. Acetaminophen and nonsteroidal anti-inflammatory drugs (NSAIDs) are allowed during the study, but not within 24 hours prior to immunization and collection of serum samples for immunogenicity. Subjects who are taking concomitant medications (3 months prior to study enrollment) to treat pre-existing conditions (e.g., hypertension) must remain on stable doses of these medications throughout the study. The doses of all concomitant medications should remain stable throughout the study, but may be changed for medical reasons as determined by the clinical investigator.

If during the study, a subject's health condition necessitates the use of any medication from those listed above, the investigator and medical monitor or designee(s), will discuss the case and determine if the subject should be withdrawn from the study. The excluded concomitant medication will be recorded as a protocol deviation. All concomitant medication including prescription and nonprescription, vitamins and natural and herbal remedies (e.g., St. John's Wort) will be documented.

Use of systemically absorbed antibiotics during the 30-day period prior to collection of the immunogenicity samples should be restricted unless clinically warranted (e.g., avoid prophylaxis) to avoid interference with the immunoassay. If a subject has been treated with any systemically absorbed antibiotics between day 1 and day 30, the day 30 follow-up visit should take place at least 7 days after the last dose of the antibiotics.

Subjects may receive other routine immunization at the 30-day follow-up visit after the completion of all study procedures at each site's discretion; however, routine vaccines should not be given in less than 30 days after study immunization.

A list of excluded concomitant medications is provided in [Appendix 12.4 List of Excluded Concomitant Medications].

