7.2.2 Per Protocol Set (PPS)

The PPS will be used to assess immunologic response and will serve as a supportive analysis. The PPS will exclude the following subjects:

- Subjects who are given antibiotics within 7 days prior to the 30-day blood draw to assess immunogenicity in the ASP3772 immunization group since these may interfere with the immunogenicity assay
- Subjects who have their 30-day blood draw 14 or more days after the 30 day post immunization scheduled blood collection
- Subjects who receive immunosuppressants as this may interfere with their ability to mount a response to the vaccine
- Subjects who have newly diagnosed immunologic abnormalities within the first 2 weeks after receiving the immunization.

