2 FLOW CHART AND VISIT SCHEDULE

Flow Chart A

Stage 1

[figure not shown]

DEC: Dose Escalation Committee; ESV: end-of-study visit; ET: early termination; PCV13: Prevnar 13; PE: physical examination.

† DEC will review day 7 data for sentinel subjects before opening full cohort.

Flow Chart B

Stage 2

DEC: Dose Escalation Committee; ESV: end-of-study visit; ET: early termination; PCV13: Prevnar 13; PE: physical examination; PPSV23: Pneumovax 23

† DEC will review day 7 data for sentinel subjects before opening full cohort

Table 1 Schedule of Assessments - Stage 1: Subjects 18 to 64 Years of Age (Group 1)

Assessments	Visit Number	Screening ^a	Dosing	Follow-up		
		1	2	3	4	5
	Visit Days (Window)	-28 to -3	1	7 (+1)	30 (± 2) [*]	180 (± 14) [§]
Informed Consent ^b		X				
Inclusion/Exclusion Criteria		X	X†			
Randomization ^c			X†			
Demographics		X				
Medical History ^d		X	X†			
Physical Examination ^e		X	X†		X	
Routine 12-lead ECG		X	X†	X	X	
Virology ^f		X				
Urine Drug Screen ^g		X	X†			
Pregnancy Test ^h		X	X†		X	
Height, Body Weight		X				
Study Immunization			X			
Vital Signs (blood pressure, pulse rate, body temperature) ⁱ		X	X†	X	X	
Clinical Laboratory Tests (hematology biochemistry, coagulation profile, hepatic profile, urinalysis) ^j		X	X††	X	X	
CCI						
Serum sample for Immunogenicity			X†		X	
Serum sample for Anti-biotin Antibodies			X†		X	X ^l
Whole-blood sample for T-cell Immune Response Measurement			X†	X	X	
CCI						
Prior/Concomitant Medication ⁿ		←			→	
Reactogenicity ^o			←	→		
AEs ^p		←			→	
SAEs ^p		←			→	
MAAEs including PIMMCs and NOCDs ^p			←		→	

Footnotes appear on next page

AE: adverse event; ECG: electrocardiogram; MAAE: medically attended adverse event; NOCD: new-onset chronic disease; **CCI** [REDACTED]; PIMMC: potential immune-mediated medical conditions; SAE: serious adverse event; WBC: white blood cell.

† To be performed prior to administration of study vaccine. **Note:** Vital signs will also be performed after the administration of the study vaccine.

‡ Not required if collected at a screening visit, which is \leq 7 days from dosing visit.

§ Visit conducted as a phone call unless anti-biotin antibodies were elevated at day 30 visit.

* If a subject has received any systemically absorbed antibiotics between day 1 and day 30, the visit should take place at least 7 days after the last dose of the antibiotics.

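### The per-protocol antibiotic exclusion is not aligned with the Day 30 visit rule: it covers any antibiotic, leaves the day-7 boundary open, and is written for the ASP3772 group only

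*SAP*

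**What the plan says.** **Visit rule.** The footnote to SAP Tables 1 and 2 begins "If a subject has received any systemically absorbed antibiotics between day 1 and day 30" and continues that "the visit should take place at least 7 days after the last dose of the antibiotics". Protocol 5.1.3 and Appendix 12.4 carry the same rule without naming a vaccine group. Protocol 5.1.3 ends it with "the day 30 follow-up visit should take place at least 7 days after the last dose of the antibiotics", having just given interference with the immunoassay as the reason for restricting these drugs.

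**Per-protocol exclusion.** SAP 5.2 excludes "Subjects who are given antibiotics within 7 days prior to the 30-day blood draw", a draw it describes as taken "to assess immunogenicity in the ASP3772 immunization group since these may interfere with the immunogenicity assay". Protocol 7.2.2 has the same wording: "Subjects who are given antibiotics within 7 days prior to the 30-day blood draw to assess immunogenicity in the ASP3772 immunization group". Neither says systemically absorbed.

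**Restatement.** SAP 7.2.1 describes the per-protocol set as including "subjects who did not receive antibiotics within 7 days of their Day 30 blood draw". It names no group and does not say that the antibiotic must come before the draw. A later bullet in SAP 7.2.1 tabulates exclusions by the reasons defined in SAP 5.2.

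**Role of the sets.** SAP 5.1 gives the primary immunogenicity analyses to the FAS, which has no antibiotic exclusion. SAP 5.2 calls the per-protocol set supportive, and SAP 7.1 and 7.2.1 foresee it only when needed.

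**The concern.** A per-protocol criterion justified by assay interference should remove the samples that the protocol itself regards as at risk, and keep the rest. This one differs from the visit rule in three ways:

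- It drops the systemic-absorption qualifier, so it reaches drugs that the visit rule does not cover.
- It leaves open whether a gap of exactly 7 days is in or out, although the visit rule permits that gap.
- It names only the ASP3772 group. A PCV13 subject drawn the day after a systemic dose stays in the set, while an ASP3772 subject with the same history leaves it.

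The per-protocol and FAS results could then differ for reasons unrelated to assay validity, and the per-protocol ASP3772/PCV13 ratios would be filtered in the numerator only. With a second wording in SAP 7.2.1, two programmers could build different sets.

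**Working it through.** The plan states no figure on this point, so there is none to reproduce. The check is a comparison of rules.

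**1. The texts side by side**

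| | Visit rule | SAP 5.2, Protocol 7.2.2 | SAP 7.2.1 |
|---|---|---|---|
| Antibiotic | systemically absorbed | any | any |
| Timing | 7 days or more from last dose to draw | 7 days before the draw, boundary not stated | 7 days around the draw, direction and boundary not stated |
| Group | none named in Protocol 5.1.3 or Appendix 12.4 | ASP3772 | none named |

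**2. Systemic antibiotics.** Let g be the days from last dose to draw. The visit rule is met when g ≥ 7. The exclusion applies when g ≤ 7 if day 7 is counted, or g < 7 if it is not.

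| g | Visit rule | Excluded, day 7 counted | Excluded, day 7 not counted |
|---|---|---|---|
| 0 to 6 | not met | yes | yes |
| 7 | met | yes | no |
| 8 or more | met | no | no |

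The rules clash at one gap only, and only on the inclusive reading.

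**3. Who lands on that gap.** With last dose on day L and the visit window opening on day 28 (30 − 2), the earliest compliant draw is max(28, L + 7).

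- L = 20 gives day 28, so g = 8.
- L = 21 to 30 gives days 28 to 37, each at g = 7.
- None of these reaches the late-draw exclusion at day 30 + 14 = 44.
- Against a day 30 target, a last dose on day 23 already has a 7-day gap. Only days 24 to 30 (7 of 30) force a later visit.

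For late courses, therefore, a subject who waits the minimum time falls exactly on the unsettled boundary.

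**4. Non-absorbed antibiotics.** The visit rule is silent on them, so the draw goes ahead on schedule. The exclusion, read literally, applies at any gap inside its 7 days. This mismatch does not depend on how day 7 is read.

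**5. Precision, illustration only.** By SAP Appendix A, the log-scale 95% half-width for one arm is proportional to t(0.975, n − 1)/√n. The number k removed from a Stage 2 dose arm of 99 is assumed, because the documents give no rate.

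- n = 99: 1.9845/9.9499 = 0.1994
- n = 97 (k = 2): 1.9850/9.8489 = 0.2015, ratio 1.0105
- Other ratios: k = 1, 1.005; k = 5, 1.027; k = 10, 1.056

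**6. After the change.** With exclusion defined as a systemically absorbed antibiotic and g < 7, no gap from 0 to 14 days is both compliant with the visit rule and excluded.

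**The case against.** The case for leaving this alone is reasonable.

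- *A per-protocol set may be stricter than a scheduling rule.* This stands. Seven days is a minimum spacing for the visit, not a stated threshold of assay validity, and Protocol 5.1.3 discourages systemic antibiotics over the whole 30 days before sampling. A reader might infer that the two rules contradict each other. The documents do not support that: for systemic drugs they differ on one day at most, on one reading of an open phrase.
- *SAP 5.2 governs.* This largely stands, because SAP 7.2.1 refers back to SAP 5.2 for exclusion reasons. The second wording is a loose summary, but it leaves doubt about whether the group limit was intended.
- *Antibiotics begun after the draw.* A reader might infer from SAP 7.2.1 that these also exclude subjects. In practice this is nearly empty, since concomitant medication is recorded only through the Day 30 visit.
- *Pre-lock review.* SAP section 1 plans a data review to verify analysis-set classification, and individual cases could be settled there. That helps, but a written rule is safer than case-by-case decisions, particularly as SAP 7.6 unblinds the sponsor for the Day 30 analyses before the final database lock.
- *Eligibility criterion 18.* It excludes anyone for whom "Subject has received any systemically absorbed antibiotics during the 7-day period prior to day 1" is true. It shares the systemic qualifier but concerns entry and sets no rule for the Day 30 draw, so it supports only the first mismatch.

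What survives is the missing qualifier, the open boundary and the one-sided group limit.

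**Conclusion.** The point holds as a misalignment of minor consequence. The missing qualifier is plain on the text. The day-7 overlap depends on reading the phrase inclusively. The restriction to ASP3772 is literal in both SAP 5.2 and Protocol 7.2.2, and is the part most relevant to interpretation, because removals affect only one side of the ASP3772/PCV13 ratio.

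Two stronger readings are not supported. A reader might infer that schedule-compliant subjects in all groups are dropped; under SAP 5.2 no PCV13 or PPSV23 subject is removed by this criterion. A reader might also infer a rate of a few percent per arm. That would need the frequency of systemic courses, the share of draws at exactly 7 days and the frequency of topical use, none of which the documents give.

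The number affected is therefore unknown. For an assumed 1 to 10 removals from 99, the loss of precision in that arm is 0.5% to 5.6% of the interval half-width. It applies to the supportive analysis only, and the primary FAS results are untouched.

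**What to change.** Use one criterion in Protocol 7.2.2, SAP 5.2 and SAP 7.2.1: *subjects in any vaccine group whose last dose of a systemically absorbed antibiotic was less than 7 days before the Day 30 blood draw*. This is the complement of the existing visit rule, which stays unchanged. State openly that the group limit is being removed, because that alters who can be excluded and is more than an editorial correction.

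The cost is one sentence in three places, agreed before analysis sets are classified. No new collection is needed: all concomitant medications are already recorded through the Day 30 visit. The documents do not say how systemic absorption will be identified in those records, so a short blinded review of the antibiotic listing may be needed to sort them.
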